6.7.6 Alkalinization and Nephrolithiasis

The frequency of persistent acidic urine will be summarized by treatment group and tested by Fisher's exact test in the ST sample. The efficacy of the alkalinization protocol to increase urine pH will be summarized overall in the ST sample. The frequency of nephrolithiasis and the absolute rate of nephrolithiasis per time exposed to study drug will be summarized by treatment group. Risk factors for nephrolithiasis will be tested in a binary generalized linear model with log link and with log time on study drug as an offset. The following risk factors will be tested in a multivariable model:

- age,
- sex,
- treatment,
- uric acid excretion fraction at baseline estimated from serum urate and 24-hr urine urate,
- uric acid crystals/hpf prior to first nephrolithiasis
 - in most recent urinalysis,
 - o average in post-randomization urinalyses,
 - o maximum in any urinalysis,
- urine specific gravity prior to first nephrolithiasis
 - in most recent urinalysis,
 - o average in all urinalyses,
 - o maximum in any urinalysis,
- urine pH prior to first nephrolithiasis

- o in most recent urinalysis,
- average in all urinalyses, and
- o minimum in any urinalysis.

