# 3.2.4.2 Modification of Uric Acid Stone Risk Factor Management Plan

The likelihood of gouty arthritis and uric acid urolithiasis – the two major known side effects of hyperuricemia –increase with age. $^{64,89,164-166}$  Accordingly, these are the main inosine-induced AEs anticipated in this study of early PD patients, who are expected to be over 60 years of age on average. $^{30,31}$  To help avoid them, any history of gout or uric acid urolithiasis will remain an eligibility exclusion criterion, as will a screening urine test result showing low pH ( $\leq$ 5.0), a major risk factor for uric acid urolithiasis. $^{29,64,87,88}$ 

Although no cases of gouty arthritis developed during SURE-PD, three subjects developed urolithiasis on inosine treatment and uric acid composition was documented in one.  Because urine pH can be readily identified and raised with common oral alkalinization treatments the phase 3 trial will employ additional measures to monitor for uric acid urolithiasis risk and a lower threshold for initiating standard alkalinization therapy. Based on SURE-PD data linking the presence of uric acid crystalluria (UAC) and low urine pH to the subsequent development of uric acid stones, urine samples provided at each visit will be processed centrally for blinded UAC determinations as well as pH measurements. These data will be followed and alkalinization will be triggered by persistently acidic urine (PAU) with or without the presence of UAC as follows (detailed in Sec. 8.4):

- Urine pH  $\leq$ 5.0 in 2 consecutive samples
- Urine pH ≤5.5 in ~3 consecutive samples (or fewer in the placebo group as needed to maintain a similar likelihood of alkalinization in the placebo and inosine groups; see Sec. 8.4.2)
- Uric acid crystalluria + urine pH  $\leq$  5.5 in 1 of the last 2 samples

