# 8.4.2 Algorithm for Triggering Urine Alkalinization Method

Based on the premise that repeated measures of urinary risk factors for stone formation will be more reliable than a single measure, 194,195 persistently acidic urine (PAU) will trigger alkalinization treatment with potassium citrate (or an alternative means of urine alkalinization were potassium citrate [51] to be contraindicated) according to the schematized algorithm of Fig. 12. The threshold for alkalinization in response to PAU is lowered by greater urine acidity (i.e., the lowest pH values), by greater persistence of lower values, and by the presence of UAC.

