#### Alkalinization Triggers

o PAU with lowest urine pH -Although the lowest urine pH value of ≤5.0 on the initial screening visit (SC1) is an enrollment exclusion criterion, it may occur at the baseline visit or as a finding in any subsequent

Figure 12. **Urine Alkalinization Flow Chart Triggers** > PAU with pH ≤5.0 (2 consecutive) > PAU with pH ≤5.5 (3 consecutive) > PAU with pH ≤5.5 (1 of last 2) if UAC low cit If cit newly low → pH ✓ in 2 wk < 6 6 - 7 full cit PAU = persistently acidic urine low cit = lower-dose potassium citrate\*\* UAC = uric acid crystals present = 10 mEq tid (<70 kg) or qid (≥ 70 kg) pH ✓ in 2 wk (using home urine sample shipped to central lab) and at next visit (when serum electrolytes, BUN, creatinine and CBC will also be checked as safety labs on cit). full cit = fuller-dose potassium citrate = 20 mEq tid (<70 kg) or qid (≥ 70 kg) stop = discontinue potassium citrate \* If pH <6 consecutively on **full cit** then reassess compliance and consult with Medical Monitor to consider increase up to 100 mEq/day potassium citrate in divided doses (tid or qid), or trial of an alternative alkalinizing agent such as sodium bicarbonate if cit not tolerated. \*\* Alternative, non-potassium alkalinizing agents such as sodium bicarbonate should be used in lieu of potassium citrate in those who have a history of peptic ulcer disease, are taking an anticholinergic agent (e.g., trihexyphenidyl), have another contraindication to potassium citrate, or do not tolerate it.

urine sample collected throughout the study. If it occurs in any two consecutive urine samples (first possible at the 3-week visit V01) it will trigger alkalinization per the algorithm outlined in Fig. 12.

o PAU with sustained lower urine pH – Three consecutive study urine pH values of ≤5.5 will trigger alkalinization (as in Fig. 12), unless the DSMB or SC determine that fewer (two) or more (four) consecutive study urine pH values of ≤5.5 will trigger alkalinization to better balance the benefits and risks of alkalinization in the trial.

o PAU with lower urine pH and UAC – If UAC is identified in the sediment of a urine sample, than a urine pH value of  $\leq 5.5$  either in the same sample or in the sample from the prior urine sample will trigger alkalinization (as in Fig. 12).

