#### • Alkalinization Impact on Blinding

Subjects and site staff will be blinded to the specific urine pH and crystalluria test results to minimize unblinding to treatment assignment. Because urate-elevating inosine treatment does not have an appreciable effect on urine pH as demonstrated in SURE-PD, the rate of alkalinization due to low urine pH will be similar in placebo- and inosine-assigned subjects, also mitigating any unblinding effect. However, a difference in alkalinization rates may occur, because UAC is expected to occur primarily in inosine-treated subjects and would further lower the threshold for alkalinization (as above). Accordingly, if alkalinization is initiated in more inosine- than placeboassigned participants then the threshold for initiating alkalinization would be altered in placebo participants in order to maintain similar frequencies of alkalinization across treatments. For example, if the number of participants in the inosine group who have initiated alkalinization exceeds that in the placebo group by 2 or >2, then the placebo group alkalinization trigger for consecutive urine pH values <5.5 even in the absence of UAC would be 2 or 1, respectively (rather than 3 as in Fig. 12). Further, the DSMB will monitor rates of alkalinization, any alkalinization AEs and any urolithiasis AEs (in aggregate and by treatment assignment) and will periodically assess whether any change in the alkalinization protocol is warranted during the study.

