6.2 Analysis Samples

The following analysis samples will be used for testing effectiveness, efficacy, safety, and tolerability endpoints:

- Intent-to-treat (ITT) Sample: Participants who are randomized, classified according to their randomized treatment assignment. Participants determined to have been ineligible prior to randomization, participants who never initiate study drug, and observations made after premature permanent discontinuation of study drug are included in this sample.
- As-treated (AT) Sample: Participants who are eligible, randomized, and take at least one dose of study drug. If a participant permanently discontinues study drug, observations made during period 1 will be censored following the first visit after study drug discontinuation. Separate analyses will classify participants in the AT sample either according to the actual treatment received or according to the average post-baseline serum urate concentration achieved. Participants randomized to inosine who report not taking inosine will be reclassified as placebo participants. Participants randomized to placebo who report taking inosine or whose serum urate during treatment averages 6.5 mg/dL or greater will be reclassified as inosine participants.

• Safety and Tolerability (ST) Sample: Participants who are randomized and take at least one dose of study drug, classified according to the actual treatment received. Participants determined to have been ineligible prior to randomization and observations made after premature permanent discontinuation of study drug are included in this sample.

The primary efficacy analyses will use the ITT sample to best estimate the expected effectiveness of urate-elevating oral inosine supplementation in clinical practice, recognizing that compliance in clinical use may differ from compliance in the clinical trial. Secondary analyses of efficacy outcomes will use the AT sample to best estimate efficacy of inosine supplementation as administered and serum urate elevation as achieved. Analyses of safety and tolerance will use the ST sample.

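### The Fisher test of persistently acidic urine compares an outcome the SAP does not define, while the placebo alkalinization trigger may be lowered to match rates between arms

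*SAP*

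**What the plan says.** SAP 6.7.6: "The frequency of persistent acidic urine will be summarized by treatment group and tested by" Fisher's exact test, in the Safety and Tolerability (ST) sample. That sample (SAP 6.2) is "Participants who are randomized and take at least one dose of study drug, classified according to the actual treatment received". Neither section defines PAU or says what happens to samples taken after alkalinization has begun.

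The protocol ties PAU to treatment. Section 8.4.2 states that "persistently acidic urine (PAU) will trigger alkalinization treatment with potassium citrate". Three routes are listed:
- two consecutive values at or below 5.0;
- a run at or below 5.5 ("Three consecutive study urine pH values of ≤5.5 will trigger alkalinization");
- uric acid crystalluria (UAC) with a value at or below 5.5 in the same or the preceding sample.

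The section 3.2.4.2 list qualifies the second route: "or fewer in the placebo group as needed to maintain a similar likelihood of alkalinization in the placebo and inosine groups". Section 8.4.2, under the impact on blinding, explains that if more inosine participants start alkalinization, "the threshold for initiating alkalinization would be altered in placebo participants in order to maintain similar frequencies of alkalinization across treatments". Its example is that when the inosine number "exceeds that in the placebo group by 2 or >2", the placebo run shortens from 3 to 2 or to 1. SAP 2.7 keeps the arrangement: unblinded statisticians run a calibrated procedure, and alkalinization rates matched between arms are part of concealment.

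**The concern.** The planned test compares the arms on a quantity that is either the matched event itself or something that event alters. Under either reading, its p-value does not answer whether urine acidity differs between arms.

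The protocol calls acidic urine a major, modifiable risk factor for uric acid stones (8.4.1) and relies on inosine having no appreciable effect on urine pH (8.4.2). SAP 2.6 reports a dosage cap prompted by more kidney stones than expected. A non-significant result could be taken as confirming the pH premise when the matching produced it. A significant result could wrongly suggest that inosine acidifies urine.

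**Working it through.** The plan gives no PAU rate, effect size or power, so there is no figure to reproduce. The check follows the rule through two possible meanings of PAU, with urine pH generated identically in both arms.

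**Inputs from the documents:** 270 participants, 135 per arm (SAP 3.8); 18 months' accrual; 11 urine samples (baseline and V01-V10); standard run of 3; placebo run of 2 or 1 when inosine starts lead by 2 or by more than 2; UAC plus one low value as a further trigger.

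**Assumptions not in the documents:** mean per-sample P(pH ≤5.5) of 0.15 or 0.30; between-person correlation 0.2 or 0.4; UAC in 0, 3% or 6% of inosine samples; alkalinization removes 80% of low readings; the ≤5.0 route is not modelled. There were 300 trials per scenario, with two-sided Fisher p < 0.05.

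Selected results with the placebo adjustment in force (P = placebo rate, I = inosine rate, Rej = share of trials rejecting):

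| P(low) | Corr. | UAC | Trigger met: P / I / Rej | Fixed run of 3: P / I / Rej | Fixed run, nobody alkalinized: Rej |
|---|---|---|---|---|---|
| 0.15 | 0.2 | 0 | 0.103 / 0.090 / 0% | 0.083 / 0.090 / 7% | 1% |
| 0.15 | 0.2 | 0.06 | 0.178 / 0.187 / 0% | 0.060 / 0.073 / 9% | 2% |
| 0.15 | 0.4 | 0.03 | 0.162 / 0.163 / 0% | 0.100 / 0.120 / 15% | 2% |
| 0.30 | 0.2 | 0.06 | 0.381 / 0.389 / 0% | 0.180 / 0.212 / 20% | 3% |
| 0.30 | 0.4 | 0.06 | 0.372 / 0.378 / 0% | 0.209 / 0.252 / 26% | 3% |

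**Reading 1, trigger met.** Over all 12 scenarios Fisher rejects in 0-1% of trials. With the adjustment switched off, the eight scenarios with UAC reject in 6-63% (for example 0.249 against 0.386, 62%). A real difference in meeting the criteria, here caused by UAC, is therefore hidden.

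**Reading 2, fixed run of 3.** Over all 12 scenarios rejection is 7-26%, against 1-6% when nobody is alkalinized. The placebo rate is lower by 0.7 points (0.090 − 0.083) to 4.3 points (0.252 − 0.209). The largest gap is 135 × 0.209 = 28.2 participants against 135 × 0.252 = 34.0.

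**Both arms are pre-empted.** With the adjustment off, the last scenario gives 0.287 on placebo and 0.246 on inosine, because UAC starts treatment before a run of 3 can form. With it on, a separate run counted participants alkalinized before three low readings: 9.4 placebo against 8.0 inosine, 15.9 against 15.2, and 29.7 against 24.0, depending on the scenario.

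**Precision.** The largest Monte Carlo standard error is √(0.26 × 0.74 / 300) = 0.025, or 2.5 points. The 7% at the low end is not clearly above 5%. A further run of four scenarios with 100 trials each gave 4%, 16%, 29% and 15%.

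**Check of the remedy.** In those four scenarios, a likelihood-based mixed model of pH was adjusted for baseline and stopped at the triggering sample. It gave arm effects of −0.011 to 0.006 SD and rejection of 3-8%. The standard error at 5% is √(0.05 × 0.95 / 100) = 2.2 points, so this is compatible with nominal.

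**The case against.** - **The headed triggers in protocol 8.4.2 are common to both arms.** What varies is called the threshold for starting alkalinization, only one of three routes varies, the change is conditional, and its counts are an example. This stands in part. A reader might infer that the protocol always manipulates the tested outcome by arm. The text supports that only if PAU means trigger met, which SAP 6.7.6 does not say. But section 3.2.4.2 puts the placebo exception inside the list of PAU criteria, and section 8.4.2 makes PAU the trigger.
- **Pre-emption is not confined to placebo.** A reader might infer that a fixed count is suppressed on placebo alone. The UAC route contradicts this: it stops runs early, mainly on inosine. Only the net direction, a lower placebo rate, survives in the simulations.
- **The SAP states no purpose for the test.** A reader might assume it is meant to show whether inosine changes urine acidity. The SAP does not say so, and a check on the matching is equally possible. This stands, but descriptive counts serve that purpose without a p-value.
- **Urine pH by arm is already planned.** SAP 4.5 and 6.7.2 summarize level and change for safety labs, and protocol 6.1.3 includes pH in urinalysis. True, but these summaries are descriptive, and later visits mix alkalinized and untreated samples.
- **Stopping at the trigger depends on the outcome and differs by arm.** This stands, and it limits which models may be used.

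**Conclusion.** The concern holds in this form. The SAP does not define PAU for this test. If PAU means trigger met, the comparison is steered toward equality by design. If it means a fixed run, alkalinization started by different routes in the two arms distorts it; under the assumed rates the placebo rate is lower and, in most scenarios, rejection exceeds nominal although urine pH is the same.

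The steering under the first reading follows from the matching rule once that rule is invoked. The sizes, and the net direction under a fixed run, rest on the assumed rates of low pH, UAC and alkalinization response. The actual distortion cannot be computed, because the documents do not report how often the placebo count was lowered. This is one secondary safety comparison with no decision rule attached, and the primary efficacy analysis is untouched. Priority is low, but so is the cost of correction.

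**What to change.** 1. In SAP 6.7.6, drop the between-arm Fisher p-value for PAU. Define PAU, and say how samples after the start of alkalinization are treated.
2. Report PAU and alkalinization starts descriptively by arm, by trigger pathway (≤5.0, run at ≤5.5, UAC) and by the placebo count in force. Note that starts are matched by design.
3. For the between-arm question, fit a likelihood-based mixed model (linear for urine pH, or logistic mixed for pH ≤5.5), adjusted for baseline pH, on on-treatment samples up to and including the triggering sample. State the missing-at-random assumption, including for stops caused by UAC. A method without likelihood protection should not be used for the binary version.
4. As a sensitivity check, compare the arms at early visits, before most alkalinization.
5. Protocol 8.4.2 gives the run criterion as ≤5.5 under the triggers and <5.5 under the impact on blinding. The two must be reconciled, and the analysis should state which was applied.

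The cost is one extra model on data already collected (urine is taken at baseline and at every on-treatment visit) and reliance on missing at random.

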## 8.5 Known Adverse Event / Experience Management Plan

#### 8.5.1 Urolithiasis

If urolithiasis occurs with symptoms of suggestive pain, hematuria or painless urolithiasis observed or if incidentally noted on imaging, the following steps should be undertaken:

- Seek prompt medical attention to diagnose and manage elimination of any stone(s)
- Medical evaluation and treatment (preferably at the time of symptom onset) should include assessment of
  - Serum urate measurement
  - o Urinalysis for pH; and initiation of alkalinization therapy as warranted
  - o Urine sediment examination for crystalluria (and type of any crystals)
  - o State of hydration assessment (by history and exam); and rehydration,  as warranted
- Submit stone, if available, for chemical analysis
- Study drug plan:
  - Suspend study drug until medical condition is stabilized (including resolution of symptoms that may be due to urolithiasis)
  - o Resume dosing if the analysis of the stone or associated sediment crystalluria indicates no uric acid or urate composition, or the subject is found not to have urolithiasis.
  - o If the analysis of the stone or associated sediment crystalluria indicates uric acid or urate composition, or is indeterminant, then:
    - Resume dosing if a remediable contributor (e.g., unduly elevated serum urate, low urine pH and/or dehydration) can be reasonably expected to be better controlled.
    - Discontinue study drug if there is no evidence of remediable source or precipitant of urolithiasis (e.g., no serum urate level above targeted range, no urine pH <6.0, no dehydration)
    - Discontinue study drug if there is evidence of remediable source or precipitant of urolithiasis but subject prefers not to continue on drug.

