2.6 Treatment Administration

Study drug will be orally self-administered in capsules containing 500 mg of inosine (active drug) or lactose (placebo). Participants will take up to two capsules three times per day (i.e., up to 3.0 gm/day) based on individualized titration that aims to achieve trough serum urate in the range 7.1 to 8.0 mg/dL in the active arm and equivalent dosage adjustments in the placebo arm. Details of the titration algorithm are specified in the clinical protocol. Note, the maximum study drug dosage was reduced from 3.0 to 2.0 gm/day beginning 24 Jan 2018 based on safety concerns over a higher than expected rate of kidney stones with greatest incidence among participants on study drug dosages greater than 2.0 gm/day.

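### SAP 6.7.6 fits nephrolithiasis with a binary log-link model and a log-time offset, which leaves fitted risk unbounded, makes the fit fragile and gives ratios below the rate ratio

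*SAP*

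**What the plan says.** SAP 6.7.6 first describes nephrolithiasis by arm, as a frequency and as an "absolute rate of nephrolithiasis per time exposed to study drug". Risk factors are then to be examined in a "binary generalized linear model with log link and with log time on study drug as an offset". On the covariates it says: "The following risk factors will be tested in a multivariable model". The list has 13 entries: age, sex, treatment, baseline uric acid excretion fraction, and three summaries of each of three urine measures (4 + 3 × 3 = 13). The urine entries run up to the event, for example "uric acid crystals/hpf prior to first nephrolithiasis", so the outcome appears to be the first stone.

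The section does not say when time on study drug ends for a participant who has a stone. It gives no expected stone count and names no fallback if the model does not fit. On the population, SAP 6.2 says: "Analyses of safety and tolerance will use the ST sample".

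Protocol 8.5.1 suspends study drug at a stone and then allows either resumption or discontinuation. One branch reads: "Resume dosing if the analysis of the stone or associated sediment crystalluria indicates no uric acid or urate composition". Another, for uric acid, urate or indeterminate stones, begins: "Resume dosing if a remediable contributor". SAP 2.6 reports a "higher than expected rate of kidney stones", without a number.

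**The concern.** The offset, and the descriptive rate just before it, show that the target is a rate per unit of drug time. A Bernoulli likelihood with a log link and a log-time offset does not model a rate coherently, because it treats the probability of a stone as proportional to time without limit. Participants with unfavourable urine values can be given a fitted risk of 1 or more. For a stone-free participant the log-likelihood contribution, log(1 - risk), is then undefined, so the fit breaks down or the coefficients are held back to stay inside the boundary.

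This is the only planned multivariable model of what drives stones, which Protocol 10.4.3 lists with gouty arthritis as the safety outcomes of greatest concern. If it does not fit, a substitute must be chosen after the data are seen. If it does fit, its ratios are too low when read as rate ratios.

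**Working it through.** **Inputs.** N = 270 randomised 1:1, so 135 per arm (SAP 3.8); 24 months of treatment (SAP 2.1). Phase 2 had three stones on inosine and none on placebo, with about 25 participants per arm (Protocol 2.2.3), so 3/50 = 6% on inosine. No stone rate for this trial is given. Assumed 24-month risks on inosine and placebo: 6%/1%, 10%/2% and 20%/5%. The upper value is borrowed from the 20% in Protocol 10.4.3, which covers uric acid stones or gouty arthritis.

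**Plan's own figure.** SAP 6.7.6 states none. The nearest is in SAP 3.9, an 80% chance of seeing an event of 1.2% incidence: 1 - 0.988^135 = 0.804. This confirms 135 per arm.

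**Form of the model.** As written, risk = T × exp(xb). Under a constant hazard, risk = 1 - exp(-T × exp(xb)). At 20% risk the cumulative hazard is -ln(0.80) = 0.223. For a covariate with hazard ratio 2 per SD (assumed), a participant 2.5 SD above the mean has 0.223 × 2^2.5 = 1.26. The true risk is 1 - exp(-1.26) = 0.72, but the model's form gives 1.26.

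**Does drug time after the stone matter?** A participant with a stone contributes log(risk) = xb + log T. The derivative with respect to b is x, so T drops out. Ending a stone former's time at the stone or at the end of drug gives the same coefficients. A simulated sample of 400,000 with a treatment-only fit confirms it:

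| Assumed risks | Binary log, time to end of drug | Binary log, time to stone | Poisson, time to end of drug | Poisson, time to stone |
|---|---|---|---|---|
| 6%/1% | 5.892 | 5.892 | 5.893 | 6.031 |
| 10%/2% | 4.932 | 4.932 | 4.932 | 5.121 |
| 20%/5% | 3.795 | 3.795 | 3.798 | 4.076 |

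The end of exposure therefore matters for a Poisson model but not for these binary coefficients.

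**Gap to the rate ratio.** From the table: 1 - 5.892/6.031 = 2.3%, 1 - 4.932/5.121 = 3.7%, 1 - 3.795/4.076 = 6.9%. The analytic risk ratio over hazard ratio with common follow-up agrees: 6/6.157 = 0.975, 5/5.215 = 0.959, 4/4.350 = 0.919.

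**Failure to fit.** Simulated trials of N = 270, 400 per row, with at least one stone in each arm. Assumed: 60% have 24 months on drug, the rest a uniform 3 to 24 months, with modest covariate effects. Failure means non-convergence, non-finite estimates, or any coefficient of 10 or more in absolute value.

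| Terms | Assumed risks | Binary log as written: failed | Fitted risk of 1 or more, or not computable | Poisson failed | Complementary log-log failed |
|---|---|---|---|---|---|
| 7 | 6%/1% | 11% | 12% | 4% | 4% |
| 7 | 10%/2% | 10% | 17% | 1% | 1% |
| 7 | 20%/5% | 15% | 65% | 0% | 0% |
| 13 | 6%/1% | 34% | 56% | 8% | 8% |
| 13 | 10%/2% | 28% | 56% | 1% | 2% |
| 13 | 20%/5% | 35% | 86% | 0% | 0% |

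Ending exposure at the stone does not rescue the binary log model: with 13 terms it then failed in 30%, 33% and 54%. Without the condition on placebo stones, mean counts were about 7.6, 12.7 and 26.1, or 0.6, 1.0 and 2.0 stones per term.

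**One stronger covariate.** Treatment hazard ratio 4, one covariate of hazard ratio 1.5 to 2 per SD, 7% to 17% stones (all assumed). The standard routine failed or reached a fitted risk of 1 in 10%, 37% and 70% of trials. Median treatment ratios were 3.79, 3.67 and 3.33, which are 5%, 8% and 17% below 4. The first-event Poisson model gave 3.99, 4.24 and 4.04.

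**The case against.** **Much of the failure is numerical.** A stone former may have a fitted value of 1 or more while the likelihood stays finite. Direct maximisation in similar one-covariate scenarios (about 9%, 11% and 19% stones, trials without a placebo stone dropped) found a finite optimum in every data set, with fitted values of 1 or more in 1%, 21% and 53%. Runs with favourable starting values and 8% to 16% stones failed in 2%, 16% and 48%. This stands: the rate of failure depends on the software and on the assumed scenario. It does not make a fitted probability above 1 acceptable.

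**A log-link binary model targets a risk ratio, which should lie below a hazard ratio.** With common follow-up that is right, and there is then no bias against a risk-ratio target. Here drug time varies, and the offset turns the coefficient into a rate-type quantity.

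**Few events for 13 terms would trouble any model.** This is partly true. With treatment alone, failures simply matched the trials with no placebo stone (35%, 10% and 0.3%) and were the same for Poisson. With 13 terms, however, the alternatives face the same events and mostly fit.

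**Tempting stronger readings.** A reader might infer from Protocol 8.5.1 that drug time after a stone is counted and dilutes the ratios. The SAP does not say that it is counted, and the score shows that it would not move these coefficients. A reader might also infer that nothing else in the plan addresses stones. SAP 6.7.6 also gives frequencies and rates by arm, and SAP 6.6.6 plans sex-specific analyses of stone risk.

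**Conclusion.** The model is wrong as written for a rate, and the defect is modest in reach. Unbounded fitted risk follows from the stated form and needs no assumption. The sizes do rest on assumptions, since the documents give no stone count and no covariate effects. Under those assumptions, the 13-term model fails in about 28% to 35% of data sets against 0% to 8% for the alternatives. The treatment ratio lies about 2% to 7% below the rate ratio with modest covariate effects, and about 5% to 17% below with one covariate of hazard ratio 1.5 to 2 per SD. The attenuation comes from the link and the boundary. The documents do not support saying that the model will usually fail, because that needs stone rates and covariate effects that they do not report. Rarity is not a safe defence either, given the statement in SAP 2.6. The analysis is secondary safety and affects no primary inference.

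**What to change.** Replace the model sentence in SAP 6.7.6 with Poisson regression for first nephrolithiasis: log link, robust standard errors, and as offset the log of time from first dose to first stone or end of study drug. A binary model with a complementary log-log link and a log drug-time offset is an alternative. Poisson is the cleaner choice, because Protocol 8.5.1 allows drug to be stopped for the stone, which makes a stone former's total drug time depend on the outcome. State that exposure ends at the first stone, both for the Poisson model and for the descriptive first-stone rate. Name a fallback, and preferably keep one summary per urine measure.

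The cost is a sentence or two and no new data. The estimand becomes a rate ratio rather than a risk ratio, and instability from few events is reduced but not removed. A Cox model is not a free substitute: the most recent, average and extreme urine values accrue after baseline and would have to enter as time-dependent covariates.
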